5.1 TIME POINTS OF OUTCOMES MEASURES

Table 2 indicates the data and study measures to be collected during the trial and at which time points across the study they are collected.

Table 1: List of outcome measures to be collected and time point of collection

Measure	Baseline	Randomisation	Ongoing	Week 1	Week 2	Week 4	Week 6	Week 8	Week 10	Week 12	Week 14	Week 16	Week 18	Week 20	Week 22	Week 24	Withdrawal	Week 24 onwards	Ext. Phase Interview ++
Consent §	X																	X	X
Screening	X																		
UDS				X	X	X	X	X	X	X	X	X	X	X	X				
LFT *	X					X				X						X		X	
BUP-XR**				X		X		X		X		X		X				X	
BUP-SL/MET **		X																	
ALC-QFM (TOP)***	X																X		
SCID-5-RV	X									X						X			X
ADAPT	X					X				X						X			
CGI-S	X																		
CGI-I						X				X						X			
CEQ-F – H***	X					X		X		X		X		X		X	X		
CEQ-F – C***	X					X		X		X		X		X		X	X		
VAS-N (H/C)***	X					X		X		X		X		X		X	X		
VAS-W (H/C)***	X					X		X		X		X		X		X	X		
DERS-SF	X					X				X						X			X
WSAS	X					X				X						X			
EQ-5D-5L	X									X						X			
AD-SUS	X									X						X			
KCF***							X			X						X			
QIDS-SR	X					X				X						X			
SURE							X			X						X			
PRO-S	X																		
PRO-I								X			X					X			
MoCA***	X									X									
OSTQOL																		X	
PHQ-4																		X	
PHQ-15																		X	
Exit Interview+																	X		
BUP-SL/MET + PSI Interview++																X			
TLFB	X	X																	X
Con Meds****		X				X				X						X		X	
Adverse Events Log		X																X	
Research Payments *****	X		X	X	X	X	X	X	X	X	X	X	X	X	X			X	
	20		10	10	10	5	10	1	10	5	10	10	10	5	10			20	

§ screening to include pregnancy test, demographics and medical history. Participants receiving XR- BUP-SL reconsented once at week 24 to continue receiving monthly injections;

* LFT for all participants at screening; during treatment for BUP-XR participants only under protocol;

** refer to section 6 of the protocol for guidelines;

*** used for mediation model;

**** ConMeds to be recorded continuously and reviewed at week 4, 12 and 24;

***** research payments are time offset to attend the clinic to complete research measures and cover travel (either a £20, £10, or £5 value, as detailed per visit applicable; loaded onto a prepaid card).

+ Exit Interview conducted at South London, Newcastle, West Midlands and Tayside sites with BUP-XR participants only. Participants will be reimbursed an additional £20 for their time in taking part in the interview (loaded onto a prepaid card).

++ BUP-SL/MET +PSI Interview conducted at South London with BUP-SL/MET +PSI participants only. Participants will be reimbursed an additional £20 for their time in taking part in the interview (loaded onto a prepaid card).

+++ Extension Interview conducted at the South London and Newcastle sites with BUP-XR participants who consented to continue treatment after week 24 between 12-24 months of them being randomised in the trial.

5.2 DEFINITIONS AND CALCULATIONS OF OUTCOME MEASURES

The following outcomes measures have been identified in relation to the objectives as described in section 3.2

Primary objective:

Objective 1 - effectiveness of BUP-XR and MET/BUP-SL

Measure 1; Number of days abstinent from 'substance' during days 8-168 (weeks 2 to 24, 161 days); combining self-report information from time-line follow-back interview adapted from the Treatment Outcomes Profile and incorporating data from 12 scheduled urine drug screens (UDS). The UDS results will provide biological verification for up to 36 out of the 161 days required.

- Days abstinent from illicit/non-medical opioids (Primary outcome)
- Days abstinent from cocaine (secondary outcome)
- Days abstinent from benzodiazepines (secondary outcome)

The primary outcome will be determined by combining the self-report results and UDS results to give an overall count for each participant. Where data is available for self-report and UDS, if the results are inconsistent the UDS data will override the self-report. Where this occurs, the result will overrule the self-report for the day of the UDS and the two days prior. Examples are indicated below.

Example 1

A negative self-report for 4 days, day 4 a positive UDS, figure 2 below.

	Day 1	day 2	Day 3	Day 4	Day 5	Day 6	Day 7	Day 8	Day 9	Day 10
Self-report	no drug use	no drug use	no drug use	no drug use	drug use					
UDS (Day 4)				positive						

Figure 2: Example 1 of Self-report and UDS results

The UDS would trump the 'no drug use' self-report for days 2 – 4, resulting the outcome in figure 3.

Outcome:	Day 1	day 2	Day 3	Day 4	Day 5	Day 6	Day 7	Day 8	Day 9	Day 10
	no drug use	drug use								

Figure 3: Self-report and UDS example 1 outcome

Example 2

A positive self-report for 2 days, day 4 a negative UDS as shown in figure 4.

	Day 1	day 2	Day 3	Day 4	Day 5	Day 6	Day 7	Day 8	Day 9	Day 10
Self-report	no drug use	no drug use	drug use							
UDS (Day 4)				negative						

Figure 4: Example 2 of Self-report and UDS results

The negative UDS would trump the self-report for days 2 – 4 (day 2 no change) resulting in the outcome below in figure 5.

Outcome:	Day 1	day 2	Day 3	Day 4	Day 5	Day 6	Day 7	Day 8	Day 9	Day 10
	no drug use	no drug use	no drug use	no drug use	drug use					

Figure 5: Self-report and UDS example 2 outcome

Example 3

UDS and self-report align figure 6, therefore no change to the outcome in figure 7

	Day 1	day 2	Day 3	Day 4		Day 13	Day 14	Day 15	Day 16	Day 17
Self-report	drug use	drug use	drug use	drug use		no drug use	no drug use	no drug use	no drug use	drug use
UDS (Day 4 and day 16)				positive						negative

Figure 6: Example 3 of Self-report and UDS results

Outcome:	Day 1	day 2	Day 3	Day 4		Day 13	Day 14	Day 15	Day 16	Day 17
	drug use	drug use	drug use	drug use		no drug use	no drug use	no drug use	no drug use	drug use

Figure 7: Self-report and UDS example 3 outcome

The syntax for calculating this variable will be validated and verified fully prior to database lock.

During a data review it was identified that some participants had been called in for their last visit early, resulting in the full primary outcome of 161 days not being obtained. The participants in question are not lost to follow up or withdrawals and are just missing due to an administration error and in most cases only by a day or two. It was noted that patient records could provide data for some of these missing days therefore, with input from independent committees, it was decided that for the TLFB data some of the final follow up days are being input based on these medical notes.

Where the TLFB data is not obtainable from the patient notes, the missing days will be imputed using a devised rule. The missing data rule used for these missing days will look at the last 14 days of data that are available for the participant, the percentage of drug use will be calculated. For all missing days a random number will be generated (either a 0 or 1, no use or use) using a probability based on their percentage used in the last 14 days.

Measure 2; Longest time in days *continuously* abstinent from 'substance' during days 8-168 (weeks 2 to 24, 161 days); combining self-report information from time-line follow-back and 12 urine drug screen (UDS) results.

- Longest count of days continuously abstinent from illicit/non-medical opioids
- Longest count of days continuously abstinent from cocaine
- Longest count of days continuously abstinent from benzodiazepines

Secondary objectives;

Objective 1 – Clinical superiority of BUP-XR plus PSI versus BUP-SL/MET plus PSI.

Will be analysed as part of phase 2 of the study and detailed in a separate SAP

Objective 2 - Safety profile

- Tabulation of AEs, ARs, SAEs, SARs and SUSARs in each group

Objective 3 - Treatment retention

- **Measure 1;** Total retention time - Days enrolled in maintenance medication for opioid use disorder (OUD) from first day following grace period (day 8) to day 168 (across 161 days weeks 2 to 24)
- **Measure 2;** Survival time - Days from randomisation to first discontinuation (i.e. time (days) enrolled in study treatment).
- ***Measure 3;** Time (days) enrolled in study treatment (retention) from week 24 to date last participant randomised plus 9 months.

*Measure 3 Will be analysed as part of the extended phase of the study and detailed in a separate SAP

Objective 4 OUD and CUD remission status

- Assessed by Standard Clinical interview for Dependence - research version (SCID-RV)
 - Remission status (Yes/No) at 12 weeks
 - Remission status (Yes/No) at 24 weeks

Objective 5 Clinician rated impression of patient response to treatment (at 24 weeks)

- **Measure 1;** Clinical Global Impression scale (severity and improvement - CQI-S/CGI-I)
- **Measure 2;** Addiction Dimensions for Assessment and Personalised Treatment (ADAPT)

Objective 6 Patient reported recovery outcomes (at 24 weeks)

Measure 1; Craving response using Craving experience questionnaire (CEQ-F)

Measure 2; Visual analogue craving rating (Need) (VAS-N)

Measure 3; Visual analogue craving rating (Want) (VAS-W)

Measure 4; Social functioning using Work and Social Adjustment Scale (WSAS)

Measure 5; Depression using Quick inventory of Depressive Symptomatology (QIDS-SR)

Measure 6; Improvement and Recovery using Substance Use Recovery Elevator (SURE)

Measure 7; Patient Reported Outcome Status (severity and improvement - PRO-S/PRO-I)

Measure 8; Emotion regulation using Difficulties in Emotion Regulation Scale short form (DERS-SF)

Measure 9; Alcohol quantity, frequency, maximum consumption (ALC-QFM (TOP) - quantity and frequency only - maximum will be reported descriptively).

Objective 7 Mediation analysis

Mediation of craving, work and social adjustment, and cognitive function on outcome.

Mediator measures;

- Visual analogue scale (VAS) for the perceived need and want for non-medical opioids and cocaine (VAS-N and VAS-W)
- Craving Experience questionnaire, frequency version (Heroin) (CEQ-F-H)
- Quick Inventory of Depressive Symptomatology – Self-Report (QIDS-SR)
- Montreal Cognitive Assessment (MoCA)
- Work and Social Adjustment Scale (WSAS)

Moderator measures;

- Sex at birth

- Age
- Current injecting status
- Centre
- Measure/Outcome baseline

Separate models will be run for each of the mediator measures using the moderator measures listed above, therefore, in total five models will be evaluated (i.e. baseline and each mediator)

Other Measures

Appendix 2 contains further details of each outcome measure and Appendix 3 contains scoring details for the relevant measures.

Many of the measures are being collected across several time points during the study, as indicated in table 2 but are only being primarily analysed here at 24 weeks. Exploratory analysis of the secondary outcomes collected at all time points other than the primary endpoint of 6 months will be detailed in a separate SAP. Additionally, the EQ5D-5L, AD-SU, PHQ-15, PHQ-4, OSTQOL and keyworker contact form are being collected but not analysed here. These measures will be used for health economic analysis and qualitative evaluation at a later date. Details on this analysis is to be included in a separate health economics analysis plan (HEAP) that will align with this SAP and signed off prior to data lock.

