10.1 Primary efficacy parameter

With a 1-week measurement grace period from randomisation, the primary endpoint is the count of days abstinent from all non-medical opioids between days 8-168 (weeks 2-24; 161 days), combined with up to 12 urine samples for opioids providing biological verification of 36 of the 161 days in the outcome measure. If the UDS shows positive, the 3 days prior to the UDS will be reported as a positive and override what is reported on the timeline follow-back interview.

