10.3 Procedures for assessing efficacy parameters

Endpoint data collection will be gathered during 13 clinic visits using the TOP (timeline follow-back [TLFB] interview) and will also include recording of cocaine and non-medical benzodiazepines. All participants will be asked to provide a urine sample during each visit. If the participant does not take a UDS then all tested drugs will be taken to be positive for the past 3 days.

10.a Assessment of Cost Effectiveness

10.1a Primary Economic Parameter

The primary economic endpoint will be the incremental cost per quality-adjusted life year (QALY) gained of injectable depot maintenance buprenorphine versus standard oral therapy, adopting a broad societal cost perspective. Incremental costs will be determined from responses to the ADSUS questionnaire and the EXPO keyworker contact form. QALYs will be calculated from EQ-5D-5L scores and by applying the EQ-5D-3L crosswalk value set. This has no implications for the sample size calculation.

10.2a Secondary Economic Parameters

There will be 2 secondary economic parameters:

- (1) Health profiles (EQ-5D-5L);
- (2) Quantities of resource use (ADSUS) and total costs disaggregated by broad categories;

10.3a Procedures for assessing cost-effectiveness parameters

The cost utility analysis will consider patient QALYs and costs from a broad societal perspective including NHS and personal social services, productivity losses (including time off work because of illness), and criminal activity. This will be based on an incremental analysis of the mean costs and QALYs for injectable depot maintenance buprenorphine versus standard oral therapy.

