4.6 MISSING DATA

Primary and secondary count-based measures For the count-based measures two situations of missing are expected. Firstly, there will be those who have missing observations periodically through the study observation period but have remained in the study for these patients multiple imputation as described above will be adopted. The memory recall for the TLFB is 3 months therefore if a patient hasn't been to visits for a couple of months recall of up to 3 months is deemed reliable [4 - 6]. Where patients have gaps in their recall on the primary outcome (at most this would be 3 months) we would use the available data to impute for the patient. Sensitivity analysis will be conducted on this imputation using a best-case worst-case analysis, see section 6.9 for more details.

Secondly, there will be some cases of participants who completely drop out of the study during the observation period i.e. withdrawals or loss to follow ups. For these patients on the primary outcome and secondary count-based measures an offset (censoring) will be used to represent different exposures rather than multiple imputation.

Furthermore, some of the primary and secondary end points (TLFB) are based on self-report and UDS tests. Where data is available for self-report and UDS, if the results are inconsistent the UDS data will override the self-report, as indicated in section 5.2. Essentially where UDS is not available this does not result directly in missing data for the outcome as the self-report

will provide this data. However, the reliability of the self-report may be impacted therefore sensitivity analysis on missing UDS data will be conducted, see section 6.9 for more detail.

Continuous outcome measures

Missing observations are expected within the dataset. For missing items within an outcome measure, the published rules for completing missing data for the relevant measure will be applied. Where there are no missing data rules for the measure, if the number of missing items on an outcome is 20% or less, then the missing value for the item will be substituted by the individual's mean score for the remaining items on the scale (Bono, Ried, Kimberlin and Vogel 2007). If there are more than 20% missing items in the scale the outcome measure will not be calculated for the participant at that time point and multiple imputation methods will be used.

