6.9 SENSITIVITY ANALYSES OR MODEL TESTING

Sensitivity analysis will be conducted on the primary analysis model including the variables that were identified as predictors of missingness as covariates in the model.

Additionally, sensitivity analysis may be required around any assumptions made for the primary analysis (e.g. outliers, data distributions) but will only be conducted if necessary. This will include a best-case worst-case analysis on the self-report missing data on the primary outcome. Best case would assume that patients did not use during any missing time periods and worst case would assume that they did use substances to evaluate any impact the imputed data may have had on the results.

Furthermore, the confidence of the reliability of the self-report will be checked by conducting a best-case worst-case sensitivity analysis on the UDS missing data for the TLFB outcomes.

For those who have a missing UDS, we will assume all missing as negative for one dataset and then for another dataset assume all missing as positive. Utilising this best –worst case scenario will provide a range of values between which the real outcome is likely to lie. The width of this range is likely to be influenced by many factors (including the COVID pandemic and not being able to collect the UDS).

Primary and secondary analysis will be conducted on an ITT basis (including all those randomised to be analysed. Sensitivity analysis may be conducted, if necessary, on protocol deviations or eligibility violations by removing them from the analysis set. This includes protocol deviations (but is not limited to) such as;

- Patients not receiving randomized allocation (per protocol analysis)
- Patients not receiving treatment within 7 days (per protocol analysis)
- Ineligible patients being randomised (mITT analysis)

Sensitivity analysis will be conducted on the patient's months in treatment (for current episode) at baseline by running the model including the variable as a factor.

Additionally, sensitivity analysis of the patient's preference of BUP-SL or MET will be conducted again by running the model including that variable as a factor. This will be conducted given that there is an adequate sample of data per group at each level of the variable (BUP-SL or MET) a sample of 50% – 60% in the MET group will indicate that we will run this sensitivity analysis.

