Finally, as indicated in section 4.6 an evaluation of missing data will be conducted prior to analysis. Missing data will be assessed by 'pandemic enrolment period' to check whether there are any differences of missingness caused by the pandemic. Missing data will be handled in line with section 4.6 of this SAP with additional guidance from recent literature on dealing with missing data in a pandemic [10].

One element of study processes which have been largely impacted by COVID is the data collection of the UDS, which will have an impact on the primary outcome. Essentially this is seen as missing data but it doesn't impact the level of missing data just the reliability of the self-report and occurs in both arms of the trial. The trial originally planned to collect UDS tests every two weeks however the following occurred;

Table 3: Summary of UDS data collection during trial following COVID-19 impacts

Site	Date	UDS data collection	
		TAU arm	Intervention arms
All	Up to 2 nd April 2020	every 2 weeks	every 2 weeks

All	2 nd April 2020 – 12 th June 2020	Not collected	Not collected
South London	04.05.2020	Not Collected	Monthly
	12.06.20	Monthly	Monthly
Newcastle	07.05.2020	Not Collected	Monthly
	29.06.20	Monthly	Monthly
Manchester	13.07.20	Monthly	Monthly
West Midlands	03.07.20	Monthly	Monthly
Tayside opened for recruitment on	27.07.20	Monthly	Monthly

As at the point of writing the SAP the trial is continuing to collect UDS monthly (on the larger visit weeks 4,8, 12, 16,20, 24). As there is little study data that hasn't been impacted by this and it has affected both arms simultaneously sensitivity analysis around this is not required. If any further changes during the ongoing pandemic occur that the investigators feel will impact any signal detected this will be conducted as exploratory post-hoc analysis.

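### SAP 5.2 lets a negative urine screen turn admitted use into abstinence in the primary count; protocol 10.1 provides an override for positive screens only, and no planned analysis removes the negative one.

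*SAP*

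**What the plan says.** **Override.** Protocol 10.1 has one rule: "If the UDS shows positive, the 3 days prior to the UDS will be reported as a positive and override" the timeline follow-back (TLFB) report. It says nothing about a negative screen. SAP 5.2 lets the screen win in any disagreement, and SAP 4.6 repeats this: "the UDS data will override the self-report, as indicated in section 5.2". Example 2 in SAP 5.2 has use reported on days 3 and 4 and a negative screen on day 4. The result is "The negative UDS would trump the self-report for days 2" to 4, so both admitted use days are scored as abstinent.

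**Window.** The protocol recodes the three days before the screen. Under SAP 5.2, "the result will overrule the self-report for the day of the UDS and the two days prior".

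**Untaken screens.** Protocol 10.3: "If the participant does not take a UDS then all tested drugs will be taken to be positive for the past 3 days". SAP 4.6 instead keeps self-report: "where UDS is not available this does not result directly in missing data for the outcome as the self-report" supplies the value.

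**Sensitivity analyses.** The UDS analysis in SAP 6.9 varies missing screens only. For the best case, "we will assume all missing as negative for one dataset"; for the worst case, all are set to positive. On the COVID-19 changes to screening, SAP 6.9 concludes that because "it has affected both arms simultaneously sensitivity analysis around this is not required".

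**The concern.** The derivation feeds the primary outcome, the cocaine and benzodiazepine counts, and the longest continuous abstinence for each substance. Three features make the negative override hard to defend as the primary rule.

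- A negative result means a concentration below the cut-off (2000 ng/ml for opiates, protocol 9.1). It does not show that reported use did not happen.
- The SAP window includes the screen day, so use later that day would be erased by a sample taken before it.
- A participant has little reason to report use that did not occur. Screening is most useful for catching use that was not reported, which is the only case protocol 10.1 covers.

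No listed analysis would show how much the rule matters. If the same rule is applied to the best-case dataset, and SAP 5.2 gives no exception, admitted use becomes abstinence in people who were never tested.

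Any bias between arms could run either way. The arm with more use days has more days to flip, while undisclosed use caught by positive screens pushes in the other direction. Screening was also not always equal: SAP Table 3 shows periods at two sites when only the intervention arms were screened.

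**Working it through.** **1. Days governed (reproduces the plan's figure).** 12 screens × 3 days = 36 of 161, as both documents state; 36/161 = 22.4%. With the monthly screening described in SAP 6.9, 6 × 3 = 18, and 18/161 = 11.2%.

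**2. Planning values (SAP 4.1).** Baseline rate 0.6 and a 23% target difference, read here as a relative increase.
- Control: 0.6 × 161 = 96.6 abstinent days, 64.4 use days.
- XR-Bup: 1.23 × 96.6 = 118.8 abstinent days, 42.2 use days.
- Difference: 22.2 days.

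**3. Effect of the negative override.** Assume use is spread evenly over the 161 days. Use days inside the 12 windows are then 64.4 × 36/161 = 14.4 (control) and 42.2 × 36/161 = 9.43 (XR-Bup). The share of these flipped by a negative screen is not in the documents, so it is varied. Change in difference = 9.43 × XR-Bup share − 14.4 × control share.

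| Control share | XR-Bup share | Change, 12 screens (days) | Change, 6 screens (days) |
|---|---|---|---|
| 10% | 10% | −0.50 | −0.25 |
| 20% | 20% | −0.99 | −0.50 |
| 10% | 20% | +0.45 | +0.22 |
| 20% | 10% | −1.94 | −0.97 |

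At 10–20%, control gains 1.4–2.9 abstinent days and XR-Bup 0.9–1.9. With 12 screens the ratio of counts ranges over 1.204–1.231, against 1.23 planned. These are scenarios, not bounds: 20% in XR-Bup and none in control gives +1.9 days, and the reverse gives −2.9.

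**4. Longest continuous abstinence.** Take a participant whose only reported use is on day 84 (week 12), with a negative screen that day. Days 8–83 give a run of 76 and days 85–168 a run of 84, so the longest is 84. After the flip it is 161.

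**5. Untaken screens, protocol 10.3 against SAP 4.6.** With 6 of 12 not taken, 18 days are set to use under the protocol. Assuming those days would otherwise be abstinent at the planning rates, this removes 18 × 0.6 = 10.8 days in control and 18 × 0.738 = 13.3 in XR-Bup. The difference between arms shrinks by about 2.5 days, or 11% of 22.2.

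**6. Equal disruption of both arms.** SAP Table 3 lists screening in the intervention arms only at South London from 04.05 to 12.06.2020 (39 days) and at Newcastle from 07.05 to 29.06.2020 (53 days). This reads the site rows as superseding the all-sites row that runs to 12 June. One or two monthly screens fall in such a period. Under the protocol 10.3 rule an unscreened control participant would lose 3–6 days × 0.6 = 1.8–3.6 abstinent days, with no counterpart in the screened arm.

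**The case against.** The strongest reply is that the protocol is silent on negative screens, and silence is not contradiction. Protocol 5.1 combines reported days with negative screens in the endpoint. Protocol 10.1 has up to 12 samples verifying 36 days, which counts every screen, not only positives. On this view the SAP filled a gap with a prespecified, symmetric rule, worked through in examples, and the 72-hour detection window matches its three days. Recall of up to three months also makes misdated use possible, and a positive-only rule cannot correct that.

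Part of this stands. The protocol does not forbid the rule, and misdating is a good reason to keep the two-way version as a sensitivity analysis. But no protocol text says that a negative screen cancels admitted use, and verifying claimed abstinence is a different operation.

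Further points are fair and limit the size of the concern:
- With equal flip rates the difference shrinks, which is conservative for a superiority trial.
- The 84-to-161 example is one constructed participant, and SAP 4.3 treats all secondary outcomes as exploratory.
- The all-positive dataset in SAP 6.9 already shows roughly what the protocol 10.3 rule would do, so that conflict will not go unseen.
- SAP 6.9 does not state explicitly that screens imputed as negative overwrite admitted use.
- The unequal screening covers two sites for some weeks during the recruitment pause, so only participants already randomised are affected.
- The two windows both span three days, offset by one.

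**Conclusion.** The concern holds and should be fixed. The SAP scores admitted use as abstinence under a rule absent from the protocol, and no listed analysis removes it. That much rests on the text alone.

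The consequence is less certain. At flip shares of 10–20%, with planning rates and evenly spread use, the 22.2-day difference moves by −1.9 to +0.5 days. This is probably small, with either sign, and the flip shares are assumptions. Longest continuous abstinence has no such limit per participant. The conflict over untaken screens is larger, at 10.8 and 13.3 days per participant when half the screens are missing, though the worst-case dataset will reveal much of it. As the documents stand, programmers working from the protocol and from the SAP would derive different primary outcomes.

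**What to change.** Before database lock:

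1. Amend SAP 5.2, Example 2 and SAP 4.6. A day counts as use if self-report says so or a positive screen covers it. A negative screen never changes a self-reported use day. Apply this to all substance counts and to longest continuous abstinence.
2. Use one three-day window, worded identically in protocol and SAP.
3. Keep the two-way override as a named sensitivity analysis, and report the number of days it flips by arm.
4. State in SAP 6.9 that a missing screen set to negative leaves self-report unchanged.
5. Reconcile protocol 10.3 with SAP 4.6 on untaken screens. The protocol rule should not be adopted wholesale: it has no exception for the telephone visits permitted in protocol 9.2, and in the Table 3 periods it would penalise unscreened control participants only.
6. Correct the SAP 6.9 statement that both arms were affected simultaneously.

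The cost is SAP wording, a protocol clarification, revised derivation syntax (which SAP 5.2 already requires to be validated before lock) and one extra run. Abstinent-day counts fall slightly in both arms compared with the current SAP rule. The target of 304 does not change.
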